**Secondary endpoints:**

1. Safety analysis: thromboembolic events and worsening renal function in TXA vs placebo

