2. LOH

3. Cost effectiveness analysis: cost saving from reduction in transfusion and LOH vs. cost of TXA administration

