#### **Safety analysis:**

Adverse events occurring in the intraoperative period, immediate postoperative period and up to 4-8 weeks after the procedure will be recorded. We will collect specific adverse events that might be related to TXA treatment, including incidence of TTE, impaired renal function (plasma creatinine increase >20% of baseline level), and neurological complications, such as seizures and vision abnormalities. Adverse events apparently unrelated to use of the drug will also be recorded. The plasma creatinine will be obtained on POD1 and preoperatively. Severe adverse events are DVT and PE.

Sections including description of the anesthesia technique, transfusion requirements and blood loss, and venous thromboembolism prophylaxis are described in the Appendix. A comparison of the frequency and severity of adverse events occurring up to the 4-8-week follow-up period will be analyzed. Any SAE will be reported to the DSMB as they occur.

**Stopping rules or safety triggers for the study:** impairment in renal function and thromboembolic events will trigger a meeting of the DSMB to discuss the events and decide on the continuation of the trial. The study will automatically be placed on hold until the investigators and the DSMB can conduct a review of events. All AEs will be collected, recorded, and analyzed. Safety oversight for this study will be provided by both the DSMB and an independent Medical Safety Monitor. If the rate of thromboembolic events or impaired renal function crosses the literature threshold or the control group with 95% probability, the study will stop.

**Postoperative drain management:** The Hemovac drain is removed when the 8h output is <50 cc. The output is recorded for every 8 hour and charted.

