### **Sample size calculation for Secondary endpoints:**

1. We do not anticipate any difference in thrombosis complications as a meta-analysis showed an OR of 0.99 (95% CI: 0.06 to 16.07).
2. Analyses for LOH will be based on the difference in mean hospital stay between the 2 groups. This will be adjusted on the number of level fused, presence of a neurological deficit, and BMI
3. Cost effectiveness analysis: The cost of TXA has to be compared with the cost reduction from shorter LOH and reduction in transfusion requirements.

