#### **Analysis of Secondary End Points:**

1. LOH: LOH will be defined from the day of surgery until the patient is medically ready for discharge. The 'actual LOH' will be defined as the duration from the day of surgery to actual discharge. The discharge will depend on the patient insurance and facility availability. The 'actual LOH' will reflect the duration of hospitalization in the general community, while the LOH will reflect the effect of TXA on improving the postoperative course of the patient. We will test for difference in mean between the 2 groups for both LOH and 'actual LOH'. A multivariable linear regression model will be used to adjust for factors related to longer LOH such as BMI, higher ASA score preoperatively, SF-36/PROMIS, and number of level fused.
2. We will analyze the cost-effectiveness of TXA by computing the cost reduction from the decreased in transfusion and LOH and the cost increase from treating TXA related side-effects: additional thromboembolic complications (cost of diagnosis and treatment). We will test for the difference in the mean between the two groups.
3. The other endpoints (cognitive assessments) are exploratory.

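### The cost analysis prices only thromboembolic complications as TXA side-effects, leaving out the renal, seizure and visual events that the protocol also lists as possibly TXA-related

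*Protocol*

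**What the plan says.** The protocol describes the cost analysis in three places.

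- Secondary endpoints, item 3: "cost saving from reduction in transfusion and LOH vs. cost of TXA administration".
- Sample size calculation for Secondary endpoints, item 3: "The cost of TXA has to be compared with the cost reduction from shorter LOH and reduction in transfusion requirements".
- Analysis of Secondary End Points, item 2: "computing the cost reduction from the decreased in transfusion and LOH", set against "the cost increase from treating TXA related side-effects: additional thromboembolic complications (cost of diagnosis and treatment". The arms are then compared on the mean.

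Only the third contains a side-effect term, and that term names one event type.

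The Safety analysis section is wider: "We will collect specific adverse events that might be related to TXA treatment, including incidence of TTE", followed by "impaired renal function (plasma creatinine increase >20% of baseline level), and neurological complications, such as seizures and vision abnormalities". The secondary safety endpoint reads "Safety analysis: thromboembolic events and worsening renal function in TXA vs placebo". Under the stopping rules, "impairment in renal function and thromboembolic events will trigger a meeting of the DSMB". The SAP does not mention the cost analysis.

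**The concern.** The protocol uses two scopes for harms that may come from TXA. The safety section lists thromboembolic, renal and neurological events, including visual ones. The cost rule prices thromboembolic complications alone. The wording after the colon is a closed list, with nothing to mark it as an example. Taken literally, a TXA patient who has a seizure work-up or treatment for renal impairment adds nothing to the side-effect term.

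Renal impairment is not a marginal event in this protocol. It is half of the secondary safety endpoint and, like thromboembolism, it triggers a data safety monitoring board (DSMB) review. The one harm that is costed is also the one the protocol expects not to differ between arms (OR 0.99, 95% CI 0.06 to 16.07). On that expectation the side-effect term would be close to zero whatever happened with the other listed events.

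At stake is one input to a secondary endpoint. The primary comparison is not affected.

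**Working it through.** The plan states no cost figure, so there is none to reproduce. The check is a comparison of the sections, followed by an accounting identity.

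**Which events are costed**

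| Event on the safety list | In the secondary safety endpoint | In the cost rule |
|---|---|---|
| Thromboembolic events | yes | yes |
| Impaired renal function (creatinine rise above 20%) | yes | no |
| Seizures | no | no |
| Vision abnormalities | no | no |

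The other two cost statements have no side-effect term, and the SAP is silent, so nothing elsewhere brings the missing costs back.

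**Amount left out, per TXA patient**

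Omitted cost = sum over omitted events of (risk on TXA − risk on placebo) × cost per event × (1 − share of that cost already counted through LOH).

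The last factor matters because LOH is itself costed: extra inpatient days caused by an event are already in the account. What remains is diagnosis and treatment beyond those days, and care after discharge. Adverse events are recorded up to 4-8 weeks after the procedure, so part of the recording window lies after discharge.

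**Illustration**

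The documents give neither rates nor unit costs. The following are assumptions: excess risk 1% to 10%, cost per event 500 to 20,000 currency units, share already in LOH 0, one half or 1.

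| Excess risk | Cost per event | None in LOH | Half in LOH | All in LOH |
|---|---|---|---|---|
| 0 | any | 0 | 0 | 0 |
| 1% | 500 | 0.01 × 500 = 5 | 2.5 | 0 |
| 2% | 5,000 | 0.02 × 5,000 = 100 | 50 | 0 |
| 10% | 20,000 | 0.10 × 20,000 = 2,000 | 1,000 | 0 |

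With the planned 50 patients per arm, a 2-point excess is one extra patient (1/50 = 0.02).

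The sign follows the excess risk. If an omitted event were less frequent on TXA, say by 2 points at 5,000 units, the same formula gives −100 and the omission would work against TXA.

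**The case against.** The strongest reply is that the omission may amount to little.

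- Renal impairment is defined by a laboratory threshold, with creatinine taken preoperatively and on POD1. A rise above 20% may need no treatment and so cost almost nothing.
- LOH runs until the patient is medically ready for discharge, so an inpatient event that delays readiness is already partly costed.
- The exclusions for seizure disorder, retinal vessel occlusion, stroke and creatinine above 1.5 mg/dL may make these events few.
- The safety list names events to collect because they might be related to TXA. It does not define what is to be costed. The protocol singles out DVT and PE as severe, so costing those alone could be a deliberate simplification, although the protocol does not say so.

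All of this bears on size, and it stands. It does not remove the mismatch: the cost rule speaks of TXA-related side-effects in general and then prices one kind.

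Three stronger readings are tempting, and the documents do not support them.

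- A reader might infer that benefits are counted in full and harms only in part, so that the net result must favour TXA. The benefits are partial too. Duration of surgery, drain time, wound complications and delirium are all objectives or endpoints, and none is costed. The direction is established for the side-effect term only.
- A reader might infer that any excess of these events overstates the saving. The event must also generate cost that LOH has not absorbed.
- A reader might infer that the omitted cost could exceed the transfusion saving. Reaching that ratio means pairing a high assumed harm with a low assumed price for the 234.61 ml difference, ignoring the LOH saving, and applying no LOH offset to the harm.

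**Conclusion.** The point holds in limited form. The cost rule leaves out three event types that the protocol itself lists as possibly TXA-related, and one of them is part of the secondary safety endpoint. If TXA raises the risk of any of them, the side-effect term is understated in TXA's favour by whatever cost falls outside LOH.

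The size cannot be derived from the documents. Under the assumptions shown it runs from 0 to 2,000 currency units per TXA patient. It is zero if there is no excess risk, if the events need no treatment, or if LOH absorbs their whole cost. The effect on net saving overall is not established, because some possible savings are uncosted as well.

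This is a cheap improvement to a secondary analysis, and confidence that it would change the result is low. A related gap belongs with it: the analysis item omits the cost of TXA and its administration, which the other two cost statements make the comparator.

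**What to change.** Rewrite item 2 of the protocol's Analysis of Secondary End Points so that it does the following:

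1. Costs diagnosis and treatment of every event on the Safety analysis list (thromboembolic events, impaired renal function, seizures, vision abnormalities), per patient and in both arms.
2. Counts each hospital day once, so that days already priced through LOH are not added again under an event.
3. Adds the cost of TXA and its administration, and aligns the wording in Secondary endpoints and in the sample-size section so that all three statements describe the same quantity.
4. Compares patient-level total cost between arms.

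Fix the list of cost items before costs are examined by arm, so that items are not chosen after the results are seen.

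The events are already recorded. The price is unit costs for three more event types, plus the TXA cost that two sections already call for. The net saving may come out smaller and its interval slightly wider.

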Cover Page for Statistical Analysis Plan

Sponsor-Investigator:	[name]
NCT Number:	NCT04272606
Unique Protocol ID:	201912099
Official Title:	Prospective, Randomized, Double Blind Study on the Effects of Tranexamic Acid on Intraoperative Blood Loss During Lumbar Spinal Fusion And Instrumentation
Date of Document:	05 December 2023

Statistical Analysis

All analyses will be conducted using R statistical software (version 4.3.1). Continuous variables will be summarized using medians and interquartile ranges and comparisons between groups will be done made using Wilcoxon rank sum or Kruskal-Wallis tests. Pairwise analyses within a group will be made using the Wilcoxon signed rank test. Categorical variables will be summarized using counts and percentages, and comparisons between groups will be performed using Pearson χ^2 test or Fisher exact test. Kendall's tau (τ) will be used as a non-parametric test of association between variables. For all analyses, the threshold for significance will be <0.05 without adjustment for multiple comparisons. Variables will be compared between groups by calculating standardized mean differences.

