**Primary Objective:**

1. To test the effect of TXA on the need for red blood cell (RBC) transfusion (intraoperatively and postoperatively) in patients undergoing lumbar spinal fusion compared to placebo (Normal Saline). This will be adjusted for number of levels to fuse, duration of surgery and patient's weight.
2. To test the effect of TXA on blood loss adjusted for weight, duration and number of level fused

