**Primary endpoints:**

1. The amount of RBC transfusion intraoperatively
2. The amount of RBC transfusion up to 7 days postoperatively
3. Measurement of intraoperative blood loss, postoperative blood loss, and total blood loss.

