#### **Analysis of Primary End Point:**

The primary endpoint is the mean difference in total blood loss, intraoperative blood loss and postoperative blood loss. An ANOVA will be used to compare between the 2 groups. A type I error rate of 0.05 will be utilized. An exploratory GLM ANOVA will be used to test for interaction for the subgroups with number of level fused, BMI and duration of surgery.

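### The documents disagree on the primary endpoint and its analysis and state no success rule, while the SAP tests everything unadjusted at 0.05, so what one significant result establishes is undefined

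*SAP*

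**What the plan says.** **Endpoint.** In the protocol, Analysis of Primary End Point reads: "The primary endpoint is the mean difference in total blood loss, intraoperative blood loss and postoperative blood loss". Transfusion does not appear there. Yet the first item under Primary Objective is "To test the effect of TXA on the need for red blood cell (RBC) transfusion". The first two items under Primary endpoints are amounts of red cells transfused, intraoperatively and then "The amount of RBC transfusion up to 7 days postoperatively". The third item bundles intraoperative, postoperative and total blood loss. The heading of the sample size section names both blood loss and transfusion as the primary endpoint.

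**Analysis.** Under Primary Objective, the transfusion comparison carries an adjustment ("This will be adjusted for number of levels to fuse, duration of surgery", and also weight), and the second objective is "To test the effect of TXA on blood loss adjusted for weight, duration and number of level fused". Analysis of Primary End Point says "An ANOVA will be used to compare between the 2 groups" and names no covariates. It adds a separate, exploratory interaction model with levels fused, BMI and duration. The SAP compares continuous variables with Wilcoxon rank sum or Kruskal-Wallis tests, has no covariate adjustment, and names no primary endpoint.

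**Error rate.** The sample size section gives a type I error of 0.05 for one test. Analysis of Primary End Point says "A type I error rate of 0.05 will be utilized", with no division across results. The SAP says "For all analyses, the threshold for significance will be <0.05 without adjustment for multiple comparisons".

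**The concern.** The stated aim is to demonstrate that TXA reduces blood loss and transfusion. For that claim a reader must know in advance which p-value carries it. Here there are three or five candidate results, depending on the section, and three candidate analyses. No section ranks the results, says that one is enough, or says that all are needed, and nothing says which analysis governs.

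At stake is the meaning of the main result. If one significant result among several can be presented as the primary finding, the trial-level false-positive rate is above the 0.05 that the protocol states. If every result must be significant, the false-positive rate is safe, but the 90% power describes one comparison and not the event called success.

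**Working it through.** **1. The plan's own figure.** The sample size section gives 40 evaluable per group for 90% power at 0.05, with 50 recruited. This cannot be reproduced from the supplied text. It depends on an SD, and the Table 2 cited for the calculation is not shown. Solving backwards, two-sided and with the normal approximation, gives a standardised difference of (1.960 + 1.282) × √(2/40) = 0.725. For the quoted blood-loss difference of 681.81 ml that is an SD of about 941 ml. Sidedness is not stated, so two-sided is assumed. Only one feature is needed below: the 90% belongs to a single comparison at 0.05.

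**2. Counting the results.** Primary endpoints: two transfusion amounts plus three blood-loss measures = 5 (my split of three numbered items). Analysis of Primary End Point: 3. One measure per domain: 2.

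**3. Any one result suffices, independent tests.** Familywise error = 1 − 0.95^k.
- k = 5: 1 − 0.95^5 = 0.226
- k = 3: 1 − 0.95^3 = 0.143
- k = 2: 1 − 0.95^2 = 0.0975

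**4. Any one suffices, correlated tests.** The outcomes are surely positively correlated, but the documents give no correlation. I assumed equal correlations of 0.3 to 0.9 and approximately normal test statistics (1,000,000 simulated draws under the null).

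| Correlation | 5 results | 3 results | 2 results |
|---|---|---|---|
| 0.3 | 0.209 | 0.136 | 0.095 |
| 0.5 | 0.183 | 0.126 | 0.091 |
| 0.7 | 0.148 | 0.109 | 0.083 |
| 0.9 | 0.102 | 0.084 | 0.071 |

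The rate falls to 0.05 only at correlation 1. These figures cover the choice of endpoint alone. The choice among three analyses is not included.

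**5. All must succeed.** Familywise error is then at most 0.05. Joint power, with each test at 90%, same simulation:

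| Correlation | 5 results | 3 results | 2 results |
|---|---|---|---|
| 0.3 | 0.660 | 0.758 | 0.822 |
| 0.5 | 0.708 | 0.782 | 0.833 |
| 0.7 | 0.760 | 0.810 | 0.847 |
| 0.9 | 0.827 | 0.850 | 0.869 |

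**6. Holm across five.** With each unadjusted test at 90% for 40 per group (standardised difference 0.725, 400,000 draws), average power per endpoint is 81% (correlation 0.9) to 85% (0.3) at 40 per group. At 45 per group, which is 50 less 10%, it is 86% to 89%.

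**The case against.** Four arguments deserve weight.

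*The hypothesis joins blood loss and transfusion with* and*, so all must succeed and no error is inflated.* This is a possible reading, and under it alpha holds. But it is the wording of a hypothesis and not a decision rule, and it leaves the 90% power detached from success. A reader might go the other way and infer that the trial's false-positive rate simply is 23%. The documents do not support that either. The inflation is conditional on an any-one rule that they never state, and 23% also needs independent outcomes.

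*The trial is Phase 2B and single-center, non-adjustment is disclosed, and the official title points to intraoperative blood loss.* All true. Disclosure does not identify the deciding result, a title does not declare an endpoint, and every section that defines the primary endpoint says more than the title does.

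*The measures overlap.* The correlation range covers this. If total loss were just intraoperative plus postoperative loss, the three-measure rate would be somewhat lower (about 0.105 at correlation 0.3), still above 0.05. The protocol's blood-loss calculations in fact call that kind of sum visible loss and derive total loss from hematocrit.

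*Adjustment is not always needed.* This stands. A reader might infer that adjusted p-values are required whatever is chosen, or that the trial must grow to 57 evaluable per group. Neither follows. A single primary, a fixed sequence or an all-must-succeed rule needs no adjusted threshold. The 57 is what a fixed 0.01 level would need for 90% power. Holm relaxes its threshold after each rejection.

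**Conclusion.** The concern holds as a defect of specification and should be fixed. The text alone establishes three things: the sections disagree on whether transfusion is part of the primary endpoint, no success rule exists, and three different primary analyses are described with none said to govern.

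The consequence depends on the missing rule. If any one result suffices, familywise error is about 10% to 21% (five measures) or 8% to 14% (three), against a stated 5%. Even one test per domain gives 7% to 9.5%. If all must succeed, alpha holds and joint power is about 66% to 83% or 76% to 85%, against a stated 90%. The direction is firm for any correlation below 1. The sizes rest on assumed equal correlations of 0.3 to 0.9, approximately normal statistics and, for power, 90% for each test.

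A reader might also infer that the sample size section lacks an SD and a defined blood-loss measure. That cannot be said: both may be in Table 2, which is absent from the supplied text.

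**What to change.** 1. Make Primary Objective, Primary endpoints, the sample size section, Analysis of Primary End Point and the SAP name the same single primary endpoint. The choice is the sponsor's and should be made and dated before results by arm are seen.
2. Give it one measurement definition. Total loss: state that it is the hematocrit-based calculation. Intraoperative loss: state whether it is the anesthesiologist's recorded estimate or the weighed quantity. Transfusion: choose one of need, amount or number, since different sections use each.
3. Name one primary analysis, and state whether it carries the adjustment for levels, duration and weight and whether it is two-sided.
4. Test one named measure from the other domain second, at 0.05, only if the first is significant. Report the remaining measures as supportive.
5. If several measures stay primary, state the rule: either all must succeed (no adjustment, power restated for joint success), or any one suffices with Holm across them.
6. In the SAP, limit the no-adjustment sentence to non-primary analyses, or add the hierarchy or rule for the primary family.

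**Cost.** Wording only, with no new data or patients. Under the fixed sequence the second claim depends on the first: both succeed in about 82% to 87% of trials if each test has 90% power. If Holm across five is chosen, average power per endpoint is about 81% to 85% at 40 per group and 86% to 89% at 45. The sponsor should confirm, against Table 2, that the 90% figure applies to the endpoint and test finally chosen.
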